**D. 10/01/2025 Amendment Summary and Rationale:**

The classification of several study endpoints is being revised. Due to the limited number of subjects enrolled, the small amount of tissue available for analysis, and the absence of prior data to inform statistical assumptions, current secondary endpoints 1 (Ki-67), 4 (gene expression), 5 (circulating DNA) and 6 (treatment planning) will now be considered exploratory in nature.

The small sample size and restricted biospecimen availability preclude adequately powered, confirmatory analyses. Furthermore, without pre-existing data to guide selection of specific genes, biomarkers, or serum markers, it is not scientifically appropriate to designate these two endpoints as definitive or hypothesis-testing. Reframing these study endpoints as exploratory allows for hypothesis generation and identification of potential signals of interest, while ensuring that study results are interpreted within an appropriate methodological context.

**a. Amendment Impact on Risk/Benefit Profile:**

This amendment does not alter the study design, subject participation, or risk/benefit profile. No additional procedures will be performed. The change pertains only to the classification and interpretation of study endpoints

**3.4 Design and Procedure:**

Prospective, single arm study in subjects with newly diagnosed ductal carcinoma in situ or invasive carcinoma of the breast

**3.5 Selection of Subjects and Sample Size:**

Women ages 60 or older with clinically node-negative, 2cm or less, biopsy proven ductal carcinoma in situ or invasive carcinoma will be considered for this trial. Women age 50-59 with a cT1N0 tumor and a low Oncotype score will also be eligible.

The final sample size is 100 subjects. Up to 150 subjects may be consented in order to enroll the target goal of 100. Given the rapid accrual of our previous trial with similar eligibility (approximately 30/32 subjects over 2 years), we anticipate completion of this trial in 5 years.

**3.6 Duration of Study:**

Subjects will be on study for approximately 3 years. Thereafter subjects will continue to be followed by the treating medical oncologist and/or radiation oncologist/mid level provider as per standard of care for follow up care.

## 4. SUBJECT ELIGIBILITY

### 4.1 Inclusion Criteria:

1. Women with a biopsy proven diagnosis of ductal carcinoma in situ or invasive carcinoma of the breast
  - a. Biopsy tissue (either slides or block) from outside institutions will be reviewed to confirm diagnosis.
2. Breast preservation candidates (no prior breast or nodal radiotherapy, no imaging evidence of multicentric or multifocal disease, no pregnant women, and no comorbid conditions precluding surgery)
3. Clinical T1N0M0 invasive carcinoma or DCIS  $\leq$  or equal to 2cm
4. 60 years of age or older or 50-59 with a low (0-17) Oncotype score . Oncotype is not required for women diagnosed with DCIS.
5. ER+, HER2- (HER2 status is not required for women diagnosed with DCIS)
6. Women of child-bearing potential must consent to use adequate contraception during the course of the study. Female subjects must agree to use a medically acceptable contraceptives including: (1) surgical sterilization (such as a tubal ligation or hysterectomy), (2) approved hormonal contraceptives (such as birth control pills, patches, implants or injections), (3) barrier methods (such as a condom or diaphragm) used with a spermicide, or (4) an intrauterine device (IUD). Contraceptive measures such as Plan B (TM), sold for emergency use after unprotected sex, are not acceptable methods for routine use.
7. WBC  $> 3000$ , Hgb  $> 9$ , platelets  $> 100000$  within 45 days of consent
8. MRI is required for radiation treatment planning on this study. A diagnostic MRI performed within 60 days of obtaining consent is acceptable and will not be repeated. Subjects who have not had a diagnostic MRI will be required to have a research treatment planning MRI with contrast ordered by a radiation oncologist; these subjects must have a GFR  $\geq 60$  ml/min.
9. Outside breast imaging will be reviewed at Duke to confirm findings are consistent with trial eligibility.

### 4.2 Exclusion Criteria:

1. Neoadjuvant chemotherapy
2. Breast implant in the breast to be treated with SBRT
3. Medical conditions that may increase risk for poor cosmetic outcome (i.e. Lupus, rheumatoid arthritis, scleroderma)
4. Subjects unable to receive study treatment planning secondary to body habitus or inability to lie flat on the stomach at length
5. HER-2+ (HER2 status is not required for women diagnosed with DCIS)
6. Positive serum pregnancy test
7. Insufficient breast imaging to judge clinical stage

8. Subjects without placement of a biopsy clip at the diagnostic procedure who are unwilling to undergo clip placement.
9. Subjects in whom treatment planning constraints cannot be met

#### **4.3 Inclusion of Women and Minorities**

Only women will be eligible for this study. Minority groups will also be eligible and accrual is expected to reflect the population of subjects seen in the Duke Multi-disciplinary Breast Cancer Clinic.

### **5. TREATMENT PLAN**

#### **5.1 Surgery:**

Surgical tumor resection will be completed within 10 days of RT delivery. Subjects will undergo intraoperative lymphatic mapping and sentinel lymphadenectomy as is standard at our institution. Standard axillary nodal dissection is acceptable if there is a contraindication to the sentinel node procedure or if felt to be clinically indicated based on nodal involvement. Omission of nodal assessment is also acceptable if clinically indicated and will not be performed in patient's diagnosed with DCIS. Resection of the tumor will include a 2mm margin of normal tissue. In general, re-excision is required for histologic margins <2mm. There may be exceptions, however, when a close margin occurs at an anatomic boundary (typically chest wall/skin) or is nearly 2mm or only focally close. Those margins are generally felt to be less significant prognostically and the role for re-excision in these cases will be made by the treating surgeon and radiation oncologist. Typically, surgical clips marking the site of tumor excision will be placed to allow for localization of the tumor bed on follow-up imaging. Standard pathologic assessment will follow.

#### **5.2 Radiation Therapy:**

##### **Target Volume:**

Prior to treatment, a biopsy clip fiducial marker will be placed in the region of the tumor to provide localization for radiotherapy delivery. Kilovoltage on-board-imaging (OBI) and/or cone beam CT (CBCT) will be used for localization as described in the section on target localization.

When required per protocol the patient will then undergo magnetic resonance (MR) imaging. The patient will be placed on the MR table with the breast pendant in a dedicated breast surface coil with arms raised overhead. Alternatively, the patient will be placed supine and specialized thoracic coils will be utilized in order to keep the breast in the same shape for the MR, CT, and radiation treatment to the extent possible. MR/CT compatible surface markers will be used to assist in this effort. T1-weighted imaging, T2-weighted imaging, inversion-recovery imaging, diffusion weighted imaging (DWI), and Dynamic contrast enhanced (DCE) MRI of the breasts will be performed. More specifically, T1 weighted MRI will be acquired with a 3D gradient-echo with spoiler (SPGR) sequence to achieve spatial resolution of sub-millimeter; T2 weighted MRI will be acquired with a 2D fast spin-echo (FSE) sequence; inversion recovery MRI will be acquired by a 2D axial short-T1 inversion-recovery (STIR) sequence; DCE-MRI will be

acquired with a 3D SPGR sequence. Before DCE-MRI acquisition, a MedRad Power Injector will be used to administer weight appropriate dose of gadolinium at 2cc/second after a 30 second inject delay.

Axial T1, axial short-T1 inversion-recovery (STIR), and dynamic VIBRANT images will be required for the delineation of the enhancing tumor, the gross tumor volume (GTV). A planning CT scan will also be acquired in order to generate dose calculations.

### **Treatment Planning and Dose:**

The MR images will be used to define the GTV. A 1.5 cm uniform expansion will be applied around the GTV to create the clinical target volume (CTV). MRI images will be fused to the CT images for further identification of normal structures and target volumes. The first 5mm of subcutaneous tissue and any chest wall (pectoralis muscle and deeper) if >1 cm from the GTV will be excluded from this volume. The first 5mm of tissue is in the photon “build-up” region and to include this area would skew the dose calculations. The chest wall is considered an anatomic boundary to tumor that is separate from the chest wall. An additional 0.5 cm margin will be applied to the GTV and CTV to create two distinct PTV volumes (PTV-GTV and PTV-CTV). PTV-GTVal and PTV-CTVal, which includes the same volumes minus the skin, will be utilized for analysis of dose coverage.. Subjects will receive a single fraction of 21Gy to the PTV-GTV and 15Gy to the PTV-CTV. This will allow for high dose to the area at greatest risk with a more moderate dose to the intermediate risk area and associated reduction in dose to the skin.

The skin, ipsilateral and contralateral lung, ipsilateral and contralateral breast tissue, spinal cord and heart will be segmented as per institutional standard and analyzed for dose. The skin will be defined as a 3 mm layer from the external body surface. The ipsilateral and contralateral breast tissue will be segmented utilizing the guidelines from ongoing phase III NRG trials. In short, the breast tissue typically included in standard breast tangents minus the lungs and chest wall will be designated the breast volume with hand modification as needed by the principal investigator/or designee.

The skin, spinal cord, and lungs will be auto-contoured in standard fashion. The heart should be contoured from the apex to the root of the great vessels. The thyroid and brachial plexus will also be contoured as appropriate depending on tumor location. The thyroid should be easily visible and contoured at the base of the neck. The brachial plexus should be visible on MRI and will be contoured with the assistance of radiology as indicated. Alternatively, the axillary vessels will be used as a surrogate for the brachial plexus.

A treatment plan utilizing arc therapy, or multiple conformal beams, or intensity-modulated therapy, or a combination of these techniques will then be designed. The beam arrangement can be organized in any fashion provided that the dose constraints listed below are met. The dose will be normalized to provide a desired coverage (95% to 98%) to the CTV.

Dose constraints are based on our phase I experience, as well as that of our Dutch colleagues (including a joint analysis of Duke/Utrecht data pending presentation/publication) and will be considered appropriate as follows:

### **Target volumes:**

**(CTV):** prescribed dose (15Gy) covers >95% of the CTV without exceeding maximum dose of 110% of prescribed dose

PTV-GT eval: ≥95% of the prescribed dose (21Gy) covers >95% volume without exceeding 110%

PTV(CTV) eval: ≥95% prescribed dose (15Gy) covers >90% of the PTV-CTV eval without exceeding 110% of prescription dose

**Normal breast:** <30% of the whole breast reference volume should receive 50% or more of the prescribed dose and <15% of the whole breast reference volume should receive the prescribed dose

- Optimal: ipsilateral breast V100% <7%; V50<21%

**Contralateral breast:** the contralateral whole breast reference volume should receive <10% of the prescribed dose to any point

- Optimal: Dmax ≤1.6Gy

**Lungs:** 1) Mean lung dose <3.6Gy 2) <37% of lung volume should receive 8Gy, 2) <1500cc to 7Gy, 3) <1000cc 7.6Gy

- Optimal: Mean ≤0.7Gy

**Heart:** 1) Mean should not exceed 1.5Gy; 2) Point dose < 5Gy.

- Optimal: Mean ≤0.6Gy, Dmax ≤3.4Gy

**Chest wall:** D20cc <16.3Gy.

- Optimal: D20cc ≤10.2Gy

**Thyroid:** maximum point dose < 10% of the prescribed dose

**Brachial plexus:** no point in the brachial plexus should receive more than 10% (2.1Gy maximum) of the prescribed dose.

**Skin dose:** 1) Maximum dose will not exceed maximum prescription dose (21Gy). 2) Dose to 1cc: <14Gy 3) dose to 10cc <9Gy

**Cord:** maximum dose to 1 cc should be 1 Gy.

In addition, a low dose survey will be performed to ensure no unanticipated regions are receiving inappropriate dose.

#### **Target Localization and Treatment Delivery:**

Subjects will be taken to the treatment machine and positioned comfortably as they were at the time of CT simulation. Image-guidance will be used to localize the treatment volume, including on-board radiographic imaging and cone-beam CT when possible. Positioning correction will be performed as necessary, verified and documented. Implanted marker may be considered as surrogates for effective target localization. The target localization procedure will be documented and adjustments will be made as appropriate. Treatment will be delivered to the target volume in one fraction. Each treatment plan will be checked for quality assurance in both calculation and dosimetry. All treatment will be recorded and verified through ARIA information system.

#### **Post-operative Treatment:**

Within 10 days, subjects will proceed to surgical resection. Pathologic assessment will be completed and reviewed per standard of care. Ki-67 will be assessed on core biopsy and definitive resection tumor (as per institutional standard) as a measure of tumor response.

Systemic therapy will only be delivered if indicated. The role for adjuvant radiation will be discussed for any patient whose pathologic assessment reveals an unanticipated high risk feature. Features judged by the multi-disciplinary treatment team to be of comparable clinical risk relative to the presenting

diagnosis (ex. a 1.8cm tumor on imaging that is just over 2cm at resection) will not necessarily require post-operative radiation. Additional radiation will be recommended to individual patients whose locoregional extent of disease is significantly greater than expected at the time of surgery (ex. nodal involvement).

Treatment volumes and prescribed doses will follow institutional standards. Hypofractionated breast treatment will be considered an acceptable alternative to standard therapy (46-50Gy) when clinically appropriate.

Subjects requiring mastectomy will be included in the correlative portion of the trial. However, their cosmesis, recurrence and late RT toxicities outcomes will be gathered and recorded separately. It would not be accurate to compare the secondary endpoints of these subjects to those receiving breast conservation.

### 5.3 Supportive Care:

Standard supportive therapies at the discretion of the treating radiation oncologist.

## 6. PATIENT ASSESSMENTS

Assessment	Pre-Tx.	Follow-up
Consent	X	
History/Physical	X	X a
Complete Blood Count (no differential)/CMP	X	
Breast imaging (mammogram minimum)	X	X a
Core Biopsy/Fiducial Markers	X b	
Planning MRI	X	
Surgical Excision with Tissue Procurement		X c
Acute Toxicity Evaluation		X d
Cosmetic Evaluation Form/Digital Photographs/QOL	X e	X e
Clinical Outcomes		X a
Serum collection	X f	X f
Urine collection	X g	X g
BRPC Consent prior to surgery		X h

- a. Physical exam by member of oncology team recommended every 4-6 months for 2 years, every 6 months through year 5 and annually years 5-10. Bilateral mammogram recommended at least annually.
- b. Verify placement of a biopsy clip at diagnostic procedure and availability of pre-treatment tissue for correlative science.
- c. Within 10 days of radiation.
- d. Appointment with the Radiation Oncologist/mid level provider 1-2 months after surgery.
- e. At baseline (prior to treatment), six months and one year after treatment and then annually for 2 additional years. Cosmetic assessment to be filled out by both patient and physician/mid level provider. Digital photographs at the same time points and at investigator's discretion.
- f. 2 lavender tubes drawn prior to radiation therapy and post radiation therapy (before surgery)
- g. Urine collected prior to radiation therapy and post radiation therapy (before surgery)
- h. Subjects will be consented to the existing Biospecimen Repository and Processing Core (BRPC) tissue collection protocol which includes safeguards to ensure adequate tissue for diagnostic evaluation and biomarker assessment

### **6.1 Screening Examination**

The screening examination can take place up to 45 days before study treatment. An informed consent must be signed by the patient before any screening procedure takes place. If however, standard of care evaluation procedures have been obtained and are within the screening evaluation time points, the SOC procedures do not need to be repeated and may be included in the screening examination. Subject data to be collected includes a complete history and physical including signed informed consent, basic clinical laboratory studies, staging and a biopsy demonstrating ductal carcinoma in situ or invasive breast carcinoma.

Assessment of the tumor by physical exam and mammogram (further imaging at radiologist/physician discretion) should include tumor measurements. Each patient will complete a baseline cosmetic evaluation as will her physician/mid level provider. QOL measures will also be assessed. Prior to study treatment, placement of a biopsy clip at the time of diagnostic biopsy will be verified as this will serve as a fiducial marker (described in section 6.2) to assist in radiotherapy localization. MRI and CT of the affected breast will then be completed for radiation treatment planning

### **6.2 Correlative Assessment**

Blood and urine will be collected at two time points, once before radiation therapy is delivered and once after radiation therapy is delivered. See Appendix VI for additional details regarding serum and urine processing and assessment. Specimens will be stored in a -80° freezer in locked facilities in the Department of Radiation Oncology for future study and analysis. The specimens may be used specifically

for this study and potentially for unspecified research. The reason, biomarkers and assays are changing rapidly. This study is expected to enroll over 5 years, during that time it is possible a new biomarker or assay could be developed that is relevant to the study of breast cancer. A study amendment would be submitted in the event of this occurring.

### **6.3 Treatment Period:**

Lumpectomy will be completed within 10 days of RT delivery. Tissue will be processed as described below in section 8.1. A second biopsy will be collected for gene expression profiling as described in Appendix 1. After preoperative treatment, the patient will be assessed 1-2 months after surgery by a Radiation Oncology faculty member/mid level provider to evaluate for acute toxicity. Subjects will go on to systemic therapy or conventional radiation if a high risk feature not anticipated pre-operatively is noted at the time of surgery. If indicated, subjects will be seen weekly during conventional treatment as is standard procedure in our department. .

### **6.4 Follow-up Period:**

Follow-up after completion of therapy will follow national guidelines and includes a history and physical every 4-6 months for the 1st 2 years, every 6 months to a year through year 5 and annually through year 10. Mammograms will be obtained at least annually. Other laboratory or radiographic studies will be obtained as directed by patient symptoms or physical exam. Quality of life and cosmetic assessments, physician/mid level provider and patient, will be performed at 6 month, 1 year, and then annually through 3 years of follow-up as will digital photographs. Local regional recurrence will be monitored on protocol at each follow-up visit.

### **6.5 Early Withdrawal of Subject(s):**

Study treatment is a one-day event thus it is not foreseeable that subjects will withdraw from protocol therapy. Extraordinary Medical Circumstances: If at any time the constraints of this protocol are detrimental to the patient's health and/or the patient no longer wishes to continue on the study long-term, the patient shall be removed from the protocol follow-up. In this event the reason(s) for discontinuation of study participation will be noted by the PI in the Radiation Oncology record.

#### **6.5.1 Criteria for Early Withdrawal**

Subjects may voluntarily withdraw from the study at any time. The PI may also withdraw a subject from the study at any time based on his/her discretion. Reasons for PI-initiated withdrawal may include, but is not limited to the following:

- Adverse events
- Abnormal laboratory values
- Abnormal test procedure results
- Protocol deviation
- Administrative issues
- Disease progression
- Pregnancy

#### **6.5.2 Follow-up Requirements for Early Withdrawal**

Standard of care follow-up will be adhered to.

### 6.5.3 Replacement of Early Withdrawal(s)

Subjects who prematurely withdraw will not be replaced unless radiation has not been initiated.

## 7. STATISTICAL METHODS AND DATA ANALYSIS

### 7.1. Amendment to the Statistical Section

The original sample size of this trial was 40 patients, and the original primary objective was to estimate the pCR rate and test the null hypothesis that the true rate was less than or equal to 0.10. The trial has been amended so that the primary objective is now the estimation of the proportion of patients with good/excellent cosmesis. Pathologic response is no longer an endpoint in this trial. These changes were necessary for two reasons. First, it was determined during the course of the trial that long-term data on cosmesis with the partial breast approach are needed regardless of the pathologic response rate. Second, since an increase in post-operative toxicity (seroma/delayed wound healing) was seen when surgery was completed 6 weeks after radiation, the amendment includes a return to surgery within 10 days of radiotherapy (as in our Phase I trial with minimal toxicity); this eliminates the opportunity to observe pathologic response. The sample size is now being increased to 100 in order to obtain a more precise estimate of the good/excellent cosmesis rate.

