### 7.2. Statistical Analysis of Cosmetic Outcome

The rate of *physician-reported* good/excellent cosmesis will be estimated at baseline and at 6, 12, 24, and 36 months. Assuming an observed good/excellent cosmesis rate of about 0.75, an increase in the sample size from 40 to 100 will allow the width of the 95% confidence interval (CI) of the rate to be decreased by 0.10 units. Specifically, a rate of 0.75 with samples sizes of 40 and 100 has 95% CI's of 0.62 – 0.88 and 0.67 – 0.83, respectively.

A true rate of good/excellent cosmesis of  $\geq 0.80$  would be considered very good, while a rate of  $\leq 0.60$  would be unacceptable. The table below gives a rough guideline for monitoring the 12 month cosmesis rate (the rates at the other time points will not be monitored).

Sample size	Review data if the number of patients with good/excellent cosmetic outcome is:
30	$\leq 21$ ( $21/30 = 0.70$ )
60	$\leq 42$ ( $42/60 = 0.70$ )
100	$\leq 70$ ( $70/100 = 0.70$ )

Simply said, any evidence that the observed cosmesis rate would likely be  $\leq 0.70$  would be cause for review. For example, suppose 30 of the first 50 patients (60%) had good/excellent cosmesis. Then even if the next 10 patients had acceptable cosmesis (40/60), this would not be enough to avoid a review of the data. Therefore, a review would have to be begun when  $N=50$ . The monitoring rules above have high probability (i.e., 0.97) of initiating a review of the cosmetic data if the true probability of having

good/excellent cosmetic outcome is  $\leq 0.60$  and a low probability (i.e., 0.14) of initiating a review if the true probability of a good/excellent cosmetic endpoint is  $\geq 0.80$ .

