## 8. SAFETY MONITORING AND REPORTING

The PI is responsible for the identification and documentation of adverse events and serious adverse events, as defined below. At each study visit, the PI or designee must assess, through non-suggestive inquiries of the subject or evaluation of study assessments, whether an AE or SAE has occurred.

Previously, an interim analysis of the first 17 patients was completed. Delayed wound healing, and an increase in grade 2 seromas, relative to our Phase I experience, were observed. The PI and study team believe that there is an interaction between the radiation and surgery (when completed 6 weeks after protocol treatment) that was not seen with our previous practice of 10 days after protocol treatment. Therefore, with the current amendment, we are returning to the practice established from our phase 1 study (Pro00015617) where minimal toxicities were observed. Whilst adverse events will continue to be monitored vigorously, it is not anticipated that those toxicities will be seen in future enrolled subjects given our prior experience. Therefore, there is no plan to complete an additional interim analysis for this study.

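### Section 7.2 does not separate patients operated on 6 weeks after radiation from those operated on within 10 days; this shifts the final cosmesis rate modestly but could materially distort the 30-patient look.

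*Combined protocol and SAP*

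**What the plan says.** Section 7.1 records that "The original sample size of this trial was 40 patients" and gives the reason for the change of schedule: "an increase in post-operative toxicity (seroma/delayed wound healing) was seen when surgery was completed 6 weeks after radiation". Section 5.1 now states: "Surgical tumor resection will be completed within 10 days of RT delivery". The new total is presented as an enlargement of the existing trial: "The sample size is now being increased to 100 in order to obtain a more precise estimate of the good/excellent cosmesis rate". Section 3.5 adds: "The final sample size is 100 subjects".

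Section 8 reports that "an interim analysis of the first 17 patients was completed", attributes the excess toxicity to an interaction between radiation and surgery at 6 weeks, and does not expect it in later patients.

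Section 7.2 estimates physician-rated good/excellent cosmesis at baseline and at 6, 12, 24 and 36 months. On monitoring it says: "The table below gives a rough guideline for monitoring the 12 month cosmesis rate". A review follows at 21 or fewer of 30, 42 or fewer of 60, or 70 or fewer of 100. The stated review probabilities are 0.97 at a true rate of 0.60 or below and 0.14 at 0.80 or above.

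Neither 7.2 nor any other section says whether patients operated on at 6 weeks are in the primary set, or at which patient the counts of 30, 60 and 100 begin. The only group whose cosmesis is recorded separately is the mastectomy patients (Section 5.2, Post-operative Treatment).

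**The concern.** One trial contains two radiation-to-surgery intervals, and the sponsor treats them as different: the first was abandoned for toxicity, and the absence of a further interim analysis is justified by the expectation that this toxicity will not recur. The primary analysis nevertheless has one denominator and one set of monitoring counts.

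Two things are at stake. The final rate will be read as describing the schedule now in use, yet part of it comes from the earlier one. And the monitoring table is most exposed at its first look, where the earliest patients weigh most. A review there could be prompted by patients on a schedule no longer given. Conversely, if the earlier patients did better cosmetically, a problem under the current schedule could be picked up late. The stated 0.97 and 0.14 assume a single rate for everyone.

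**Working it through.** **Inputs from the documents.** Original size 40 (7.1); final size 100 (3.5, 7.1); 17 patients in the interim analysis (8); planning rate 0.75, review limits 21/30, 42/60 and 70/100, reference rates 0.60 and 0.80 (7.2).

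**Assumptions.** The number operated on at 6 weeks is taken as 17, the only figure available. Patients are counted in enrolment order. Cosmesis rates by schedule are not given anywhere, so a range is shown.

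**Step 1: reproduce the plan's figures.** The interval is p ± 1.96 × √(p(1 − p)/n).
- n = 40, p = 0.75: 0.616 to 0.884, width 0.268.
- n = 100, p = 0.75: 0.665 to 0.835, width 0.170.

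These match the stated 0.62–0.88 and 0.67–0.83. Exact sequential binomial probabilities for the review rule, with one rate for all patients:

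| True rate | Review at 30 | By 60 | By 100 |
|---|---|---|---|
| 0.80 | 0.129 | 0.142 | 0.144 |
| 0.60 | 0.906 | 0.975 | 0.994 |

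The stated 0.14 reproduces. The stated 0.97 matches the first two looks; over all three the value is 0.99.

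**Step 2: share of earlier patients if pooled.** 17/30 = 57% at the first look, 17/60 = 28% at the second, 17/100 = 17% at the end.

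**Step 3: effect on the final rate.** Pooled rate = (17 × old + 83 × current)/100.
- Old 0.60, current 0.80: (10.2 + 66.4)/100 = 0.766, a shift of −3.4 points.
- Old 0.70, current 0.80: (11.9 + 66.4)/100 = 0.783, a shift of −1.7 points.
- Old 0.80, current 0.60: (13.6 + 49.8)/100 = 0.634, a shift of +3.4 points.

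**Step 4: effect on monitoring.** Same exact recursion, with the first 17 patients at the old rate and the rest at the current rate.

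| Old rate | Current rate | Review at 30 | Any look |
|---|---|---|---|
| 0.80 | 0.80 | 0.13 | 0.14 |
| 0.75 | 0.80 | 0.23 | 0.25 |
| 0.70 | 0.80 | 0.36 | 0.38 |
| 0.60 | 0.80 | 0.63 | 0.65 |
| 0.60 | 0.60 | 0.91 | 0.99 |
| 0.80 | 0.60 | 0.51 | 0.95 |

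**Step 5: precision for the current schedule alone.** With 100 − 17 = 83 patients and p = 0.75, the interval is 0.657 to 0.843, width 0.186, against 0.170 at 100.

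**The case against.** The case for leaving the plan alone has real force.

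- **Inclusion is inferred.** The plan never says who makes up the 100 or the first 30. Section 8 does not say that all 17 had surgery at 6 weeks, nor how many were enrolled before the change. This stands, so the defect is an undefined analysis set. It still needs an edit, because every sentence on sample size describes one continuing trial.
- **No cosmesis difference is shown.** Seroma and delayed wound healing are post-operative toxicities, and the Appendix II physician scale allows seroma in an excellent result if appearance is unchanged. This stands: the sizes above are scenarios. But the same scale also scores scar tissue, fibrosis and contour defect, so an effect on cosmesis is plausible.
- **Pooling may suit the question.** The hypothesis in 3.1 concerns 21 Gy given preoperatively and names no surgery interval. This supports keeping the pooled estimate, though not leaving it unaccompanied.
- **The table is only a rough guideline.** Crossing it triggers a review, and reviewers could look up surgery dates. This softens the consequence, but the stated 0.97 and 0.14 are still offered as properties of the rule.
- **Excluding treated patients after seeing their toxicity would itself be data-driven.** This stands and argues against simply dropping them from the primary set.

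A reader might go further and infer that neither the primary result nor the monitoring describes the current regimen. The documents do not support that. With 17 earlier patients, 83% of the final set is on the current schedule, and the shift of 1.7 to 3.4 points lies inside the half-width of about 8.5 points at n = 100.

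**Conclusion.** The point holds as a missing definition with a cheap remedy. Followed as written, on the natural reading, the primary rate mixes two schedules that the sponsor regards as different, and more than half of the first monitored group could come from the earlier one.

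The consequence for the final estimate is modest. The consequence for the first look could be material in either direction: a false prompt when the current schedule is performing well, or a delayed one when it is not. In the second case the overall chance of a review stays high (0.95 against 0.99), so the loss is mainly time. The stated operating characteristics apply only if both schedules share one rate.

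These sizes rest on 17 earlier patients, counting in enrolment order, and assumed schedule-specific rates. A larger earlier group would increase both effects. If the two schedules have equal cosmesis, there is no distortion. This should be fixed, but it does not invalidate the trial's main estimate.

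**What to change.** Amend Section 7.2 as follows.

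1. At every time point, report the good/excellent rate with its 95% CI by surgery schedule, next to the pooled estimate. Base any conclusion about the current schedule on the patients operated on within 10 days.
2. Apply the 12-month counts to the within-10-days patients, or show the counts by schedule at each look. State at which patient the count starts. If only 83 such patients exist, the last look needs a restated limit; at the plan's own proportion of 0.70 this is 58 or fewer (0.70 × 83 = 58.1).
3. State the number treated on each schedule and the resulting precision: for example 0.66–0.84 (width 0.186) if 83 remain, against 0.67–0.83 (width 0.170) for 100.
4. Say that 0.97 and 0.14 assume one common rate, or recompute them for the set actually monitored.

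The data are already collected and no extra accrual is needed. The cost is a slightly wider interval for the current-schedule estimate (by 0.186 − 0.170 = 0.016) and, if the counts are restricted, a later first look. Keeping the pooled estimate in the report avoids the appearance of discarding patients because of their toxicity.
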